University of Sao Paulo

**DEVELOPMENT OF A MOBILE APPLICATION TO PROMOTE SELF-CARE IN PATIENTS
WITH FIBROMYALGIA**

[name]

[name]

The study protocol was registered at ClinicalTrials.gov.

Registration No.: NCT0300491

Sao Paulo

July 14th 2014

Objectives

The purpose of this work was to develop a mobile application software for the promotion of self-care and assess the effectiveness of its use during six weeks on health-related quality of life, symptoms and self-care agency of patients with FMS, and to compare the results to the use of a paper book of similar content. Secondarily, patients' adherence to ProFibro app was evaluated.

Methods

A randomized, single-blind, controlled trial was conducted in the Physical Therapy Clinical Research and Electromyography Laboratory at the Physical Therapy, Speech Therapy and Occupational Therapy Department of the School of Medicine of the University of São Paulo (USP), in the city of São Paulo, Brazil. The project was approved by the Research Ethics Committee of the School of Medicine, University of São Paulo (No. 274/14).

Participants (eligibility criteria)

Volunteers were identified using the USP Newspaper and related social media. After answering a screening questionnaire sent by email, potential participants were invited to a face-to-face assessment to confirm eligibility. All participants signed a written informed consent prior to entering the study.

The study included adults and middle-aged individuals (19-59 years) diagnosed with FMS, according to the 2010 American College of Rheumatology (ACR) diagnostic criteria¹, who were smartphone users and completed elementary education. Exclusion criteria were: individuals undergoing physical therapy or treated in the last three months; diagnosis of other conditions causing chronic pain (neuropathies, rheumatoid arthritis, osteoarthritis, spinal stenosis or cancer); severe mental disorders (schizophrenia, psychosis, bipolar affective disorder, severe depression); hearing or visual impairment.

Sample Size

The sample size was calculated to detect the minimal clinically important difference (MCID) of 14% between two groups in health-related quality of life, measured by the FIQR, with a standard

deviation of 24.3.^{2, 3} Calculations indicated that a sample size of 30 participants would provide a power of 80% at a level of significance of 5%. Five participants were added to each group to compensate for possible dropouts, resulting in a total of 40 participants.

Randomization

Participants were randomly allocated into Experimental and Control Groups. A physical therapist who was not involved in the trial concealed a computer-generated random sequence in sequentially numbered, opaque, sealed envelopes.

Outcomes

An outcome assessor blinded to the interventions enrolled participants in the trial and evaluated them at baseline and after six weeks of intervention.

At baseline, the following demographic and clinical data were collected: age, sex, marital status, level of education, family income, duration of the syndrome and use of medication.

The primary outcome was health-related quality of life measured by the Brazilian Portuguese version of the FIQR.^{3, 4} The FIQR has 21 questions based on an 11-point numeric rating scale of 0 to 10, with 10 being 'worst'. All questions are framed in the context of the past seven days. The FIQR is divided into three domains: (a) Function (contains nine questions), Overall Impact (contains two questions), and (c) Symptoms (contains ten questions regarding pain, stiffness, lack of restorative sleep, poor energy, anxiety, depression, tenderness, memory, balance and environmental sensitivity). The Function score is the sum of the nine questions divided by 3 (range 0 to 30), the Overall Impact score is the sum of two questions (range 0 to 20), and the Symptoms score is the sum of the ten questions divided by 2 (range 0 to 50). The total FIQR is the sum of the three domain scores (range 0 to 100).

Secondary outcomes were: pain measured by the Widespread Pain Index (WPI)¹ and the Visual Analog Scale (VAS)⁵; severity of symptoms measured by the Symptom Severity (SS) Scale¹; agency of self-care measured by the Brazilian Portuguese version of the Appraisal of Self-Care Agency Scale – Revised (ASAS-R)^{6, 7}.

The WPI is one of the diagnostic variables of the 2010 ACR diagnostic criteria for FMS. It is a measure of the number of painful body regions (range 0 to 19) in the context of the past week.

The VAS for pain was used to measure the pain intensity (range 0 to 10) at the moment of the examination. It is a continuous scale comprised of a 10-cm horizontal line, anchored by two verbal descriptors: no pain (score of 0) and worst imaginable pain (score of 10).

The SS Scale is another diagnostic variable of the 2010 ACR diagnostic criteria. It is a 4-component scale (range 0 to 12) composed of assessor-rated cognitive problems, unrefreshed sleep, fatigue and somatic symptom count. The timeframe for the assessment of the SS Scale is one week.

The ASAS-R is a multidimensional measure that evaluates the level of self-care agency regarding having, developing and lacking the power for self-care (range 15 to 75). It comprises 15 items responded in a five-point Likert scale ranging from 1 (totally disagree) to 5 (totally agree).

ProFibro app was programmed to register the date and time of each access to the app functions. Patients' adherence to the use of ProFibro app was assessed according to the number of accesses to the app functions after six weeks.

Interventions

A physical therapist researcher who was not involved in the outcome assessment opened the sealed envelopes and assigned participants to each group.

At their first individual session, the researcher gave the participants of the Experimental Group a smartphone with the ProFibro app installed, and the participants of the Control Group a paper book of similar content to that of the mobile app. The book was made after the development of the mobile app was completed.

Both groups received a 20-min introductory tutorial leading the participants through the main functions of the mobile app or book chapters. For further instructions, the information icon of the app functions and tutorial video in the menu were presented to the participants of the Experimental Group. Finally, the participants were instructed to explore and use the tools for six weeks with a view to self-care.

Statistical methods

Primary and secondary outcomes were compared to baseline in each group and between groups. Change scores (the difference between the final and the baseline score) were used for comparison between groups. Analysis was performed on an intention-to-treat basis, with data carried forward from the baseline assessment in case of dropouts. Kolmogorov-Smirnov and Levene tests were used to verify normality and equality of variance of the data, respectively. Independent t tests were used with variables that were normally distributed, and Mann-Whitney rank sum tests were used with variables that were not normally distributed. A p-value <0.05 was considered statistically significant. These statistical tests were performed using software SigmaStat 3.5 (Systat Software, Inc, Erkrath, Germany).

In the analysis of clinical important changes, participants were classified as respondents if they scored higher than the MCID for an outcome, and non-respondents otherwise. The MCID for the FIQR total score was considered a change score of 8.1, and for VAS pain a change score of 2.^{2,8} For the other variables, no MCID was yet identified, and a change score of 15% was used.¹⁰

Funding

This work was supported by the Sao Paulo Research Foundation (FAPESP No. 2014/17547-5)

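### The stated 80% power does not follow from the stated inputs: 30 participants with SD 24.3 give about 33% for 14 points and about 14% for the plan's own 8.1-point MCID

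*Combined protocol and SAP*

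**What the plan says.** The Sample Size section gives the target: "The sample size was calculated to detect the minimal clinically important difference (MCID) of 14% between two groups in health-related quality of life". The instrument is the FIQR and the assumed SD is 24.3. The section then says "Calculations indicated that a sample size of 30 participants would provide a power of 80% at a level of significance of 5" per cent. On the allowance for losses and the final size it says: "Five participants were added to each group to compensate for possible dropouts, resulting in a total of 40 participants". Under Outcomes, the FIQR total runs from 0 to 100.

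The Statistical methods section compares the groups on change scores, by independent t test or Mann-Whitney test, on an intention-to-treat basis with baseline values carried forward for dropouts. "A p-value <0.05 was considered statistically significant". For the responder analysis the same section says: "The MCID for the FIQR total score was considered a change score of 8.1". Both sections cite reference 2.

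The plan does not state whether the test is one- or two-sided, the allocation ratio, the sample-size formula, what the 14% is a percentage of, whether 24.3 is the SD of a single score or of a change, or any correlation between baseline and follow-up.

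**The concern.** A 14-point difference against an SD of 24.3 is a standardised difference of a little under 0.6. Fifteen per arm is far too few to detect an effect of that size with 80% power. The plan also uses the label MCID for two figures, 14% and 8.1 points, without linking them, and the smaller one makes the shortfall worse.

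The FIQR is the primary outcome and the comparison with the paper book is a stated objective. If the trial is presented as having 80% power, a non-significant result invites the reading that the app is no better than the book. On the stated figures the design could not separate no difference from a full MCID in either direction.

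**Working it through.** **Inputs.** Difference 14% (Sample Size), read as 14 points on the 0–100 FIQR (Outcomes). SD 24.3, N = 30, power 80% and alpha 5% (Sample Size). MCID 8.1 points (Statistical methods). Assumed because not stated: two-sided test, 1:1 allocation, and 24.3 as the SD of the analysed change score.

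**Arm size.** 30 + 2 × 5 = 40, so 30 is the two-arm total, or 15 per arm. Had 30 been per arm, the total would be 2 × (30 + 5) = 70.

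**Attempt to reproduce the 80%.** Standardised difference d = 14/24.3 = 0.576. The noncentrality is d√(n/2) = 0.576 × √7.5 = 1.58 on 28 degrees of freedom. Two-sided power is 33.2% (normal approximation 35.1%). The 80% is not reproduced.

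**Required size.** Normal approximation: n per arm = 2 × [(1.96 + 0.8416) × 24.3/14]² = 47.3, so 48. By the t distribution it is 49 per arm, 98 in total.

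**The 8.1-point MCID.** d = 8.1/24.3 = 0.333. Power with 15 per arm is 14.3%, and 143 per arm are needed for 80%. The two MCIDs coincide only if 14% is relative to a baseline mean of 8.1/0.14 = 57.9 points. Any baseline mean below 100 makes 14% smaller than 14 points, so under a relative reading 33% is the most favourable figure.

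**Other readings, 14 points, SD 24.3.**

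| Reading | Two-sided power | One-sided power |
|---|---|---|
| 15 per arm | 33.2% | 45.8% |
| 20 per arm (all 40 complete) | 42.7% | 55.7% |
| 30 per arm (contradicts the total of 40) | 59.3% | 71.2% |

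A one-sample or paired test reaches 80% with 26 participants two-sided, or 21 one-sided. Neither is 30, and neither addresses the between-group question.

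**If 24.3 is a single-visit SD.** With equal SDs at both visits and correlation r, the change-score SD is 24.3 × √(2(1 − r)). The plan gives no r, so a range is shown for 14 points with 15 per arm:

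| Assumed r | Change SD | Power |
|---|---|---|
| 0.3 | 28.75 | 25% |
| 0.5 | 24.3 | 33% |
| 0.7 | 18.82 | 50% |
| 0.8 | 15.37 | 67% |

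With 15 per arm, 80% power needs d = 1.060. That means a change SD of 14/1.060 = 13.2, and r = 1 − 13.21²/(2 × 24.3²) = 0.85. For 8.1 points the SD would have to be 7.64, with r = 0.95.

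**What the design delivers at SD 24.3.**

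| | 15 per arm | 20 per arm |
|---|---|---|
| Power, 14 points | 33% | 43% |
| Power, 8.1 points | 14% | 18% |
| Difference detectable with 80% power | 1.060 × 24.3 = 25.8 points | 0.909 × 24.3 = 22.1 points |
| 95% CI half-width, t × 24.3 × √(2/n) | 2.048 × 8.873 = 18.2 points | 2.024 × 7.684 = 15.6 points |

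**The case against.** The strongest point is that the analysis uses change scores and the plan does not say what kind of SD 24.3 is. If it is a single-visit SD, 33% is exact only at r = 0.5, and a strong correlation would raise it. That stands as a condition on the exact figure. It does not rescue the 80%, which needs r of about 0.85 with the 30 participants to whom the plan attaches its claim, and no correlation or SD of change is given.

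A second point is that intention-to-treat with baseline carried forward keeps all 40 in the analysis. With no dropouts, power is 43%, slightly more than half the claimed figure, and r of about 0.80 would suffice for 14 points. But if five per arm drop out, each contributes a change of zero. The expected difference shrinks to 0.75 × 14 = 10.5 points, and simulation puts power at about 29–33%, depending on the mean change in each arm. The dropout allowance does not close the gap.

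Third, 8.1 is used as a within-person responder threshold, which is a different quantity from a between-group difference, and the plan claims no power for 8.1 points. That is fair, so the 14% figure is secondary. The plan nevertheless calls both values the FIQR MCID and must say how they relate. The 33% result does not depend on this.

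Finally, the documents do not show how the error arose, nor do they say that a null result would be read as equivalence. The first is left open here; the second is a foreseeable risk, not something the plan states.

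**Conclusion.** The concern holds. On the stated inputs, 30 participants give about 33% power for 14 points, against the 80% claimed, and the required total is 98 before dropout. For the 8.1-point MCID, power is about 14%. These figures assume a two-sided 5% t test, equal allocation, 14% meaning 14 points, and 24.3 as the SD of change. Changing the sidedness, the arm size or the basis of the percentage leaves power below 80% in every case tried. The one route to 80% with 30 participants is a change-score SD near 13.2, which the plan neither states nor supports. The detectable difference of 25.8 points is more than three times the 8.1-point MCID (25.8/8.1 = 3.2). Because this is the headline power claim for the primary outcome, it must be corrected.

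**What to change.** Replace the 80% statement with what the design delivers, for example: with 15 evaluable participants per arm and a change-score SD of 24.3, a two-sided 5% t test has 33% power for a 14-point FIQR difference and 14% for 8.1 points; the difference detectable with 80% power is about 26 points. Give the 20-per-arm figures alongside (43%, 18% and about 22 points), noting that baseline carried forward would dilute them if participants drop out.

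State what kind of SD 24.3 is, what the 14% is a percentage of, the sidedness and the allocation ratio. If a smaller change-score SD was in fact assumed, give it with the correlation behind it and show the calculation.

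State the MCID once, in FIQR points, and use it in both the sample-size and responder sections; if two values are intended, explain why the group-level and individual-level figures differ.

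Report the between-group FIQR difference with its 95% confidence interval against the 8.1-point MCID, and state that p ≥ 0.05 will not be read as equivalence to the book.

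The cost is wording only, with no extra participants. The stated power becomes much less favourable, and the between-group comparison would have to be described as exploratory.

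### The primary between-group comparison takes no account of baseline FIQR, and no stratification on it is described, so chance imbalance among 40 patients costs precision and clarity; adjusting for baseline would recover much of this at no cost.

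*Combined protocol and SAP*

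**What the plan says.** The Randomization section states random allocation to two groups and adds that "A physical therapist who was not involved in the trial concealed a computer-generated random sequence in sequentially numbered, opaque, sealed envelopes". It gives no type of randomization, allocation ratio, block size or stratification factor, and no other section does. The Sample Size section works with a fixed number per arm: "Five participants were added to each group to compensate for possible dropouts, resulting in a total of 40 participants". The eligibility criteria set no FIQR range.

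For the analysis, the Statistical methods section says: "Change scores (the difference between the final and the baseline score) were used for comparison between groups". The test is an independent t test, or a Mann-Whitney test if the variable is not normally distributed. No baseline covariate enters either one. Dropouts have their baseline value carried forward, so their change is zero.

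Two figures give the scale. The Sample Size section uses a standard "deviation of 24.3" for the FIQR, without saying whether it is the SD at baseline, at follow-up or of change. The Statistical methods section says "The MCID for the FIQR total score was considered a change score of 8.1", as a threshold for classifying individual patients.

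**The concern.** With about 20 patients per arm and a widely spread primary outcome, the arms can start visibly apart by chance. The two usual protections are stratifying the allocation on the baseline score and adjusting for it in the analysis. The plan describes neither.

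A change score is often thought to settle the matter because it subtracts each patient's own baseline. It does so fully only if baseline and final scores are perfectly correlated. Otherwise the arm that starts worse is expected to improve more through regression to the mean, and the comparison favours that arm. At stake are the precision of the app-versus-book estimate and how readily it can be interpreted if the baseline table shows a gap.

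**Working it through.** **Inputs.** From the documents: 40 patients in two groups, taken as 20 per arm; SD 24.3; 8.1 points, used here only as a yardstick for a gap; unadjusted change scores. Assumed, because the documents are silent: 24.3 is the between-patient SD at baseline and also at week 6; the correlation rho between the two is 0.5 to 0.8; scores are normal.

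**1. The plan's own figure.** The Sample Size section seeks to detect a "minimal clinically important difference (MCID) of 14% between two groups in health-related quality of life, measured by the FIQR", and says "Calculations indicated that a sample size of 30 participants would provide a power of 80" percent. Reading 14% as 14 points on the 0 to 100 scale, with two-sided 5%:

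n per arm = 2 × (1.960 + 0.842)² × 24.3² / 14² = 47.3, so 48 per arm, 96 in total.

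The stated 30 is not reproduced. Fifteen per arm would need an SD of 14 × √(15/2) / 2.802 = 13.7. That is a separate problem. It matters here because the plan's arithmetic does not show what kind of SD 24.3 is, so the results below are given over a range.

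**2. Chance of a baseline gap above 8.1 points.** SE of the gap = SD × √(2/20); P = 2 × [1 − Φ(8.1/SE)].

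| Baseline SD | SE of gap | 8.1/SE | P |
|---|---|---|---|
| 24.3 | 7.68 | 1.05 | 29.2% |
| 20 | 6.32 | 1.28 | 20.0% |
| 18 | 5.69 | 1.42 | 15.5% |
| 15 | 4.74 | 1.71 | 8.8% |
| 13.7 | 4.33 | 1.87 | 6.1% |

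This already takes a 20:20 split as given. In simulation at SD 24.3, blocks of 4 alone give 29.3% and an unrestricted sequence 29.8%. Blocks within two strata of baseline FIQR give about 9%.

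**3. What the change score leaves behind.** Given a baseline gap D, the expected error in the change-score difference is (rho − 1) × D. For D = 8.1:

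- rho 0.5: −0.5 × 8.1 = −4.05
- rho 0.7: −0.3 × 8.1 = −2.43
- rho 0.8: −0.2 × 8.1 = −1.62

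Higher FIQR is worse, so the sign favours the arm that starts worse. Over all randomizations D averages zero, and so does this error.

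**4. Precision with and without adjustment (SD 24.3, 20 per arm).** Change score: SE = 7.68 × √[2(1 − rho)]. ANCOVA on baseline: SE = 7.68 × √(1 − rho²), times √(1 + 1/36) = 1.014 for estimating the slope from 40 patients.

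| rho | SE, change score | SE, ANCOVA | Variance saved |
|---|---|---|---|
| 0.5 | 7.68 | 6.75 | 23% |
| 0.7 | 5.95 | 5.56 | 13% |
| 0.8 | 4.86 | 4.67 | 7–8% |

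Simulation agrees to within about 0.1 point.

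**5. Does stratifying add precision once ANCOVA is used?** Hardly. In simulation the ANCOVA SE goes from 6.71 to 6.65 at rho 0.5 and from 5.53 to 5.52 at rho 0.7.

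**The case against.** The best defence is that the plan is valid as it stands. Unstratified randomization with a change-score comparison is unbiased over repeated randomizations and holds its type I error, and stratifying a single-centre trial of 40 is a matter of taste. All of that stands. So does the point that the correlations are assumed, and that the gain is small if rho is 0.8 or more.

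Three stronger readings are tempting but not supported:

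- A reader might infer that the sequence was unrestricted. The documents do not say so; they leave the type unstated, and the fixed number per group fits a restricted list at least as well. If it was unrestricted, an exact 20:20 split would occur 12.5% of the time, 24:16 or worse 27%, and an arm of 14 or fewer 8%. Those figures apply only in that case.
- A reader might blame the 29% on the lack of blocks. Blocks equalize arm sizes, not FIQR; only stratification or a similar method acting on the score lowers it.
- A reader might think that an 8.1-point gap passes into the result. The change score removes the raw gap, and only the regression-to-the-mean part remains.

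The 29% is also the top of a range, because 24.3 is unlabelled, and 8.1 is a threshold for individual change rather than a criterion for imbalance.

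What the defence does not answer is why a baseline score that is already collected should be left out of the comparison.

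**Conclusion.** The point holds as a missed, free improvement, not as a validity failure. Neither the described allocation nor the primary comparison deals with chance imbalance in baseline FIQR. The probability of a gap above 8.1 points is about 29% if 24.3 is the baseline SD, and falls to 6–20% for SDs of 13.7 to 20. When such a gap occurs, the change-score comparison is off by an expected 2.4 to 4.1 points at correlations of 0.7 to 0.5, which is 30% to 50% of 8.1. Adjustment saves about 13% to 23% of the variance at those correlations and 7–8% at 0.8. These figures rest on equal SDs at both visits, normal scores and 20 per arm. The missing description of blocks is a reporting gap only and would not carry the point by itself.

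**What to change.** Replace the unadjusted t test or Mann-Whitney test on FIQR change with one pre-specified linear model: week-6 FIQR (or change; the group estimate is the same) on group and continuous baseline FIQR. Report the adjusted difference with its 95% confidence interval. Check normality and equal variance on the residuals, and name in advance what is done if they fail, for example a permutation test of the group term in the same model. This needs no extra data, patients or visits, only a short change of text. If outcome data have already been examined by group, report the model as a labelled sensitivity analysis.

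State the type of randomization, the allocation ratio, and any blocks or strata.

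Optionally, if allocation has not begun, use permuted blocks within two strata of baseline FIQR, with the cut fixed in advance. This limits visible imbalance and keeps the arms near 20:20, but adds little precision once the model is used. It costs a second series of envelopes and totalling the FIQR before allocation. Block ends become slightly more predictable, but the enrolling assessor is blinded and a different researcher opens the envelopes. The stratum does not replace the continuous baseline score in the model.

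### App adherence is defined only as a number of accesses, which cannot show whether use was sustained over six weeks, and the plan does not say whether tutorial accesses are excluded

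*Combined protocol and SAP*

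**What the plan says.** The Objectives section of the combined protocol and SAP names adherence as a secondary aim, for the app only: "adherence to ProFibro app was evaluated". The end of the Outcomes section describes the data, "ProFibro app was programmed to register the date and time of each access to the app functions", and then the measure, which is the "number of accesses to the app functions after six weeks". It gives no threshold, no breakdown by day or week and no date from which counting starts.

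The Interventions section describes the first session: "Both groups received a 20-min introductory tutorial leading the participants through the main functions of the mobile app or book chapters". In addition, "the information icon of the app functions and tutorial video in the menu were presented to the participants of the Experimental Group". After that, "the participants were instructed to explore and use the tools for six weeks". No frequency of use is prescribed.

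The Statistical methods section opens with "Primary and secondary outcomes were compared to baseline in each group and between groups". It gives no method for adherence, and adherence is not in the list of secondary outcomes in the Outcomes section.

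**The concern.** Participants were asked to use their tool over a six-week period, so the natural question for an adherence aim is whether use continued across that period. A number of accesses answers a different question, namely how much use there was altogether. A participant who tries everything in the first few days and then stops can score the same as one who returns steadily to the end. The plan collects the timestamps that would separate these two and then names a summary that does not draw on them for that purpose. This is therefore a matter of the chosen measure as well as of missing detail.

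The second gap is where counting begins. Participants are taken through the app's main functions in the first session, and no rule says whether the accesses made then belong to adherence. If they do, a participant who never opened the app again would still have a count above zero.

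What is at stake is the interpretation of the adherence result, and with it any statement that the app was, or was not, used for the intended period.

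**Working it through.** The plan states no adherence figure, so there is none to reproduce. The check is a reading of the text plus two illustrations. The access numbers in both are assumptions, because the documents contain no access data.

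**1. Does a count identify sustained use?**

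Input from the plan: six weeks of use, 6 × 7 = 42 days. Assumed total: 42 accesses for one participant.

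| Assumed pattern | Total | Active days | Active weeks | Last day of use |
|---|---|---|---|---|
| 42 accesses on day 1 | 42 × 1 = 42 | 1 | 1 | 1 |
| 6 a day in week 1 only | 6 × 7 = 42 | 7 | 1 | 7 |
| 1 a day throughout | 1 × 42 = 42 | 42 | 6 | 42 |

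The count is the same in all three rows, while active days run from 1 to 42 and active weeks from 1 to 6. Splitting the count by app function would not help, because each function's count has the same ambiguity.

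**2. What if accesses in the introductory session are counted?**

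Let t be the accesses made in that session and L those made afterwards. The share of the count that comes from the session is t / (t + L). Neither t nor L is in the documents. Assume t from 5 to 20:

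| Later accesses L (assumed) | t = 5 | t = 20 |
|---|---|---|
| 10 | 5/15 = 33% | 20/30 = 67% |
| 42 | 5/47 = 11% | 20/62 = 32% |
| 200 | 5/205 = 2% | 20/220 = 9% |

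For any fixed t the share rises as L falls, so light users are inflated most in relative terms. The spread from 2% to 67% comes entirely from the assumed inputs. It shows that the size cannot be determined from the plan and is not an estimate of it.

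**3. Could the plan's own data settle both questions?**

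Yes. Timestamps allow distinct days and weekly use to be derived, and allow accesses in the introductory session to be removed. The limit lies in the stated summary, not in the data collected.

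**The case against.** The strongest reply is that the Objectives section says only that adherence would be evaluated. It does not promise to show persistence, and with no prescribed frequency an access count is a legitimate description of use. Adherence is not a listed secondary outcome and no test depends on it. This stands as a limit on importance, and it rules out judging participants against daily use. It does not rescue the count as a sole measure, because the instruction to participants is framed over six weeks and a count is silent on that dimension.

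Three stronger readings are tempting but are not supported.

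- **A reader might infer that tutorial use is counted as adherence.** The documents do not say so. The instruction to use the tools comes after the tutorial in the text, so a window that opens after the session is a natural reading, and the timestamps would permit it. Equally, no exclusion is stated. Moreover, if every participant made the same number of tutorial accesses, this would be a constant offset: it would leave the ranking of participants unchanged and distort only levels and ratios.
- **A reader might infer that the plan pools everything into one total and discards the dates.** The wording also fits counts per function, and the dates may serve to bound the six-week window. What can be said is that no date-based measure is specified.
- **A reader might fault the lack of any use measure for the paper book.** The adherence aim is restricted to the app, and no planned analysis relates outcome to use, so this is not a defect of the app measure. Asking about tool use at the six-week evaluation could also reveal allocation to the blinded assessor.

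**Conclusion.** The point holds in a narrow form and is minor. As stated, the measure cannot show whether app use was sustained over six weeks: the same count of 42 is compatible with 1, 7 or 42 active days. That conclusion needs no assumption about actual use, since it follows from what a count is; the 42 accesses are only an example. The plan also leaves open whether accesses in the introductory session are excluded. Any resulting inflation would be conditional on their being counted, would weigh most on low users in relative terms, and cannot be sized from the documents.

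The consequence is limited to a descriptive secondary aim. The primary FIQR comparison, the listed secondary outcomes and the responder analysis do not use the access data and are not affected.

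**What to change.** In the adherence paragraph of the Outcomes section:

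- State that counting starts after the introductory session, and remove accesses logged before that point.
- Report for each participant the number of distinct days with at least one access.
- Report use in each of weeks 1 to 6, so that any decline is visible.
- Keep the number of accesses as a supplementary description of intensity.
- Say whether opening the information icons or the tutorial video counts as an access.

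Active days should be presented as a description, without a pass mark, because the plan sets no frequency of use.

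The cost is a little more analysis of logs that the app already records, with no new data collection and no added burden on participants. The downside is that adherence may look lower than a count would suggest.
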